4.2 Discussion of Study Design, Including the Choice of Control Groups

[Redacted content]

5 SELECTION OF STUDY POPULATION**5.1 Inclusion Criteria**

- (1) Signed informed consent from one of the parent(s)/legal representative(s).
- (2) Subjects, both genders, aged 3 to 60 months.
- (3) Subjects with acute diarrhea (defined as the passage of three or more unformed or liquid stools within the last 24 hours and lasting for less than 3 days).

5.2 Exclusion Criteria

- (1) Known allergy to Racecadotril or any of its ingredients.
- (2) Subjects suffering from renal or hepatic impairment.
- (3) Subjects with fever > 39 degrees Celsius
- (4) Subjects with bloody and/or purulent stools.
- (5) Subjects suffering from antibiotic (e.g. amoxicillin)-associated diarrhea, chronic diarrhea or iatrogenic diarrhea.
- (6) Subjects with alternating bouts of diarrhea and constipation.
- (7) Diarrhea due to exacerbation of chronic gastrointestinal diseases such as irritable bowel syndrome, irritable bowel disease or pancreatic exocrine insufficiency.
- (8) Cystic fibrosis or coeliac disease.
- (9) Subjects suffering from prolonged or uncontrolled vomiting.
- (10) Subjects with rare hereditary problems of fructose intolerance, glucose-galactose malabsorption syndrome or sucrase isomaltase insufficiency.
- (11) Subjects having received antibiotic treatment within 2 weeks prior to start of the current diarrhea episode.
- (12) Subjects having received antidiarrheal drugs (except pre- or probiotics see section 7.7.) 48 hours prior to Day 1.
- (13) Subjects with severe dehydration requiring intravenous fluid or electrolyte replacement or hospitalization treatment.
- (14) Subject with a history of angioedema or who had reported angioedema with angiotensin converting enzyme inhibitors (such as captopril, enalapril, lisinopril, perindopril, ramipril)
- (15) Subjects with combined diseases or medical situations that would prevent to be enrolled into the study, depending on the judgment of the investigator
- (16) Intake of experimental drug within 30 days prior to study start.
- (17) Subjects with contraindications to ORS or susceptible to the warnings of ORS.

6 REMOVAL OF SUBJECTS FROM THERAPY OR ASSESSMENT

All subjects are free to withdraw from participation in this study at any time, for any reason, specified or unspecified, and without penalty or loss of benefits to which the subject is otherwise entitled.

The Study Termination form must be completed for all subjects who did not fail screening, those who completed and those who prematurely terminated the study and an end of treatment visit should be performed.

In case of premature termination of the subject from the study, the primary reason for this premature termination is to be indicated according to the following definitions:

- Adverse event: discontinuation due to any adverse event (AE) with a corresponding entry reflected on the Adverse Events form in the CRF
- Lack of efficacy: subject fails to respond to the study drug at an acceptable level where the subject or the Investigator feels it is in the best interests of the subject to seek another treatment.
- Lost to follow-up: the subject's parent(s)/caregiver(s)/legal representative(s) fails to return to the study site for scheduled visits and does not respond to telephone or written attempts to contact.
- Withdrew consent: subject's parent(s)/legal representative(s) decides to stop subject's participation in the study for any reason other than an AE, or is unable to complete the study as described in the clinical study protocol (e.g., subject is relocating to another location).
- Administrative: the Sponsor decides to discontinue the study (either at the study site or the entire study), e.g., general safety problems leading the Sponsor to entirely stop the study.
- Protocol violation – anything which is in direct violation of the clinical study protocol (e.g., inclusion/exclusion violation).

Subjects will terminate the study at the discretion of the investigator and will undergo further diagnosis and alternative treatment under the following conditions.

1. If the subject needs alternative treatments or rescue medication which are prohibited concomitant therapies in this study
Any comedication which may interfere with the evaluation of the efficacy parameters of this study should be avoided (see section 7.7).
Subjects who cannot complete the study duration of five days without continuous intake of concomitant medication or who need rescue medication should be withdrawn. The investigator should consult with the CRO/sponsor prior to withdrawal of the subject.
2. If the subject develops fever > 39 degrees Celsius (> 39 degrees Celsius in two repeated measurements within one hour)
3. If the subject develops bloody and purulent stools
4. If the subject has watery stool more than 10 times per day showing signs of apathy

5. If the subject's disease state worsens, e.g. dehydration or increased vomiting
6. If the subject needs hospitalization

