8.3 Other Assessments

Informed Consent

Voluntary written informed consent must be obtained from one parent/legal representative prior to performing any study-related procedures (see Section 1.3).

Demographic Data

Demographic data (gender, age, year and month of birth, race) will be collected for all subjects.

Medical History

Any clinical event, including diagnosis, condition, or surgery, that occurred prior to allocation to treatment, is to be recorded on the Medical History form. In case a clinical event concerns a chronic disorder, which means it started in the past and it is still present at the screening visit, it should also be recorded on the Medical History Form. Examples of these events are diabetes, migraine, and hay fever.

Concomitant Medication

All medication taken by the subject during the study (from signing the informed consent form through post-study follow-up) is to be recorded on the Concomitant Medication form, except for study drug.

Subject Diary

The parent(s)/caregiver(s)/legal representative(s) have to document date and time of each individual stool of the subject and the stool consistency (watery, normal) of each evacuation continuously. The subject individual stool consistency before start of the diarrhea is defined as normal (e.g. taking into account the age and diet, e.g. breast feeding, of the individual subject).

Recording can be stopped after the excretion of two consecutive normal stools or no stool within 12 hours.

The date, time and dose of study drug intake as well as the amount ORS consumed has to be recorded.

Fever will be measured twice daily, once in the morning and once in the evening with at least 12-hour interval using the same device and method (preferably ear temperature), by the parent(s)/caregiver(s)/legal representative(s) and documented in the diary including method, time and value.

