10.3 Efficacy

The primary efficacy variable is the duration (hours) of diarrhea (treatment duration max 5 days). Duration of diarrhea is defined as date of the evacuation of the last watery/diarrheal stool before recovery or end of treatment.

The primary parameter, duration of diarrhea, will be analyzed using descriptive statistics. In addition, a Kaplan-Meier plot will be generated for which summary statistics will be presented as well.

The secondary efficacy variables are

- Time until recovery, defined as date and time of the evacuation of the first of two consecutive normal stools or no stool within 12 hours after the first normal stool.
- Number of subjects recovered; in total and until each individual treatment day
- Mean and median time until recovery
- Assessment of treatment success by the physician:
The assessment of treatment success by the physician will be done using the Global Physician Assessment.

GPA score:

- 1 = Complete relief of acute diarrhea,
- 2 = marked improvement of acute diarrhea,
- 3 = moderate improvement of acute diarrhea,
- 4 = slight improvement of acute diarrhea,
- 5 = no change in acute diarrhea,
- 6 = worsening of acute diarrhea.

Treatment will be rated as success when the GPA score equals 1 or 2.

- Number of stools at baseline and per treatment day for toilet-trained subjects, only.
- Number of watery stools per day for toilet-trained subjects, only.

Secondary efficacy parameters will be analyzed similarly to the primary analysis. All parameters will also be summarized using descriptive statistics.

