9.1 Primary Efficacy Variable

The primary efficacy variable is the duration (hours) of diarrhea (treatment duration max 5 days). Duration of diarrhea is defined as date and time of the evacuation of the last watery/diarrheal stool before recovery or end of treatment. The duration of diarrhea definition can be referred to Figure 9-1. The primary efficacy parameter, duration of diarrhea, will be analyzed using descriptive

statistics. In addition, a Kaplan-Meier plot will be generated for which summary statistics will be presented as well. The KM algorithm will be applied to derive the median duration (hours) and the 95% confidence intervals for the median, and mean duration. The censored number and event number will be presented as counts and percentage as well.

The SAS code is listed as below:

PROC LIFETEST DATA=duration METHOD=KM PLOTS=SURVIVAL (FAILURE ATRISK); TIME T*status (0); RUN;

[figure not shown]
Note:

[figure not shown]
The proc lifetest analysis will be performed with failure curve (an increasing trend). The duration (hours) of diarrhea or time (hours) until recovery is recorded in the variable T. The variable status is the censoring indicator. A status of 1 indicates an event time, and a status of 0 indicates a censored time. The event is recovery. The censored data are those did not recover during treatment period including drop-outs. When a patient doesn't recover beyond the end of study (treatment duration maximal 5 days), duration is stopped at the end of study date and it will be regarded as a censored data as well. The censored times will be plotted as a plus sign on the Kaplan-Meier.

An event time for the duration of diarrhea is defined as the duration from the date of dosing to the date of the evacuation of last watery/ diarrheal stool before recovery. A censored time for the duration of diarrhea is defined as the duration from the date of dosing to the date of not recovery during treatment period.

An event time for time until recovery is defined as the time from the date of dosing to the date of the evacuation of the first of two consecutive normal stools or no stool within 12 hours after the first normal stool. A censored time for time until recovery is defined as the duration from the date of dosing to the date of not recovery during treatment period.

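### A child withdrawn early for treatment failure can enter the primary descriptive summary with a short duration of diarrhea, and Kaplan-Meier censoring removes only part of that bias

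*Protocol*

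**What the plan says.** **Leaving the study.** Protocol Section 6 lists conditions such as prohibited or rescue treatment, worsening and ("If the subject needs hospitalization") admission, under the lead-in "Subjects will terminate the study at the discretion of the investigator and will undergo further diagnosis and alternative treatment under the following conditions". On rescue it adds: "Subjects who cannot complete the study duration of five days without continuous intake of concomitant medication or who need rescue medication should be withdrawn". Protocol 7.7 repeats that children needing a listed medication leave the study. Lack of efficacy is one of the premature-termination reasons.

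**The diary.** Section 6 asks for a termination form, including for "those who prematurely terminated the study and an end of treatment visit should be performed". The flow charts (Protocol 8.6, SAP 3.8) collect the diary at the end-of-treatment visit. The only written rule for stopping entries, in Protocol 8.3 and similarly in 4.1, is recovery: "Recording can be stopped after the excretion of two consecutive normal stools or no stool within 12 hours".

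**The primary variable.** Protocol 10.3: "Duration of diarrhea is defined as date of the evacuation of the last watery/diarrheal stool before recovery or end of treatment". SAP 9.1: "Duration of diarrhea is defined as date and time of the evacuation of the last watery/diarrheal stool before recovery or end of treatment". Protocol 10.3 then says "The primary parameter, duration of diarrhea, will be analyzed using descriptive statistics", with a Kaplan-Meier plot in addition; SAP 9.1 keeps that order.

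**Children who do not recover.** SAP 9.1 makes recovery the Kaplan-Meier event, censors unrecovered children and drop-outs, derives a median with 95% CI and a mean, and reports event and censored counts. SAP 5.2 takes the last available on-treatment value as the efficacy endpoint. It also stops an unrecovered child's duration, as censored, at the end of study, with treatment lasting at most 5 days. The full analysis sample keeps any treated child with one post-baseline efficacy assessment.

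**The concern.** Stopping racecadotril and leaving the study are treated as one event. A child withdrawn on Day 1 or 2 because the diarrhea worsened reaches end of treatment on that day, so the last watery stool before that point is an early one. Entered into a plain mean or median, that time looks like a fast cure. The error runs in the favourable direction: failure shortens the reported duration.

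Two features make this worth settling in advance. The trial has one arm, so there is no control group in which the same error would offset. And if stools are not recorded after withdrawal, no later analysis can recover how long those children had diarrhea.

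**Working it through.** **1. The plan's own figure.** The stated precision is 3.1 percentage points for 99% recovery with n = 40: 1.96 × √(0.99 × 0.01 / 40) = 0.0308, which agrees. It concerns the proportion recovered after 3 days, not the duration of diarrhea, so it neither supports nor weakens this point.

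**2. Inputs.** From the documents: 40 completers, at most 48 recruited (8 of 48 = 16.7% for drop-outs of every kind), and a maximum of 5 days, taken as 5 × 24 = 120 h. Assumed, because the documents do not give them: the mean duration in recovered children, the number of failures and their times.

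**3. Effect on the plain mean.** Take 40 recovered children with mean 36 h and k failures each entered at t hours: mean = (40 × 36 + k × t) / (40 + k).

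| k | t = 12 h (last watery stool before withdrawal) | t = 72 h | t = 120 h |
|---|---|---|---|
| 1 | 1452/41 = 35.4 | 1512/41 = 36.9 | 1560/41 = 38.0 |
| 4 | 1488/44 = 33.8 | 1728/44 = 39.3 | 1920/44 = 43.6 |
| 8 | 1536/48 = 32.0 | 2016/48 = 42.0 | 2400/48 = 50.0 |

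Against 36 h, failures entered at 12 h lower the mean by 0.6, 2.2 and 4.0 h. The gap between the 12 h and 120 h columns is k × 108 / (40 + k) = 2.6, 9.8 and 18.0 h. The row k = 8 is a ceiling, since the allowance of 8 covers all drop-outs.

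**4. How much Kaplan-Meier repairs.** Assume 40 children in total, of whom k are withdrawn at 24 h. The others recover with lognormal durations (median 36 h, log-SD 0.7, capped below 120 h). Medians in hours:

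| k | Plain, at withdrawal | Plain, failures at 120 h | KM, censored at withdrawal | KM, unrecovered to 120 h |
|---|---|---|---|---|
| 1 | 35.2 | 36.8 | 36.0 | 36.0 |
| 4 | 32.7 | 39.7 | 36.9 | 38.7 |
| 8 | 28.8 | 45.0 | 39.1 | 43.7 |

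The plain and Kaplan-Meier medians use slightly different conventions, so compare like with like. For k = 4 the plain median is 7.0 h too low (39.7 − 32.7), and the Kaplan-Meier median censored at withdrawal is 1.8 h too low (38.7 − 36.9). For one failure the Kaplan-Meier median does not move. The corresponding means for k = 4 are 42.0 h (plain), 45.1 h (KM censored at withdrawal) and 51.6 h (failures at 120 h).

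The last column does not depend on 120 h being the true duration. The Kaplan-Meier median is the same for any failure time beyond the median, because those children are still in the risk set when the median is reached.

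**5. Which time does the SAP give a withdrawn child?** SAP 9.1 counts censored time to the date of non-recovery during treatment, which has no clear meaning for a child who left on Day 2. SAP 5.2 points to the 5-day cut-off in one sentence and to the last on-treatment value in another. These give different answers for the same child.

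**The case against.** The strongest reply is that the SAP does not treat these children as recovered. Recovery is the event, drop-outs are censored, the censored count is shown, and SAP 4.3 and 9.1 take a mean and a median from Kaplan-Meier. This stands, and it limits the problem. A reader might infer that failure certainly lowers the headline mean and median. The documents do not support that: they never say that an uncensored mean or median will be the headline, or which time a withdrawn child receives in it. Protocol 8.5 gives recovery as the only closing point, and SAP 5.2 can be read as carrying the child to the cut-off. Against this, Protocol 10.3 and SAP 9.1 both name end of treatment as a closing point and put descriptive statistics first. The short value is therefore the natural reading, though not the only one.

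A reader might also infer that the protocol ends the diary at withdrawal. No sentence says so. It is an inference from collection of the diary at the end-of-treatment visit and from the absence of any provision for later entries. Termination is also at the investigator's discretion, not automatic.

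The size is assumed. The plan expects at least 99% recovery after 3 days, about 0.4 unrecovered of 40; if that holds, the bias is small. Other outputs (termination reasons, proportion recovered with CI, physician assessment) would still show failures, and no hypothesis test rests on the mean. All of this stands.

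Finally, giving 5 days to every early stopper would bias the result upward for a child who relocated or whose consent was withdrawn. This is right, and the rule should separate failures from other drop-outs. Continued recording would also measure duration under whatever treatment followed, and the report should say so.

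**Conclusion.** The point holds in a limited form. The plan has no rule for withdrawal due to failure in the primary summary. Followed as written, the plain summary can count such a child as a short duration. Kaplan-Meier censors the same child as if withdrawal were unrelated to prognosis, at a time the SAP does not define. That removes part of the bias, not all of it.

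Under the assumed 36 h mean, the plain mean falls by 0.6 h with one failure entered at 12 h and by 2.2 h with four; with four failures it would be 43.6 h at 120 h instead of 33.8 h. These are illustrations: the result depends on the number and timing of failures, which the documents do not give. With none, nothing changes. The change should be made because it is cheap and because stools not recorded cannot be supplied later.

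**What to change.** 1. **Protocol Section 6 and 8.3.** Separate stopping study drug from ending stool recording. Unless consent is withdrawn, the caregiver continues the existing diary to recovery or Day 6. Because the diary is collected at the end-of-treatment visit, arrange its return, or collection of the stool information, around the existing safety call. When the drug stops and what care is given are unchanged.

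2. **Protocol 10.3 and SAP 9.1.** Do not enter the last watery stool before withdrawal as a completed duration for an unrecovered child. Take the headline median from Kaplan-Meier. If continued-diary data are missing:
   - keep children withdrawn for lack of efficacy, rescue, worsening or hospitalization as unrecovered to the 5-day cut-off (120 h);
   - censor other drop-outs, such as relocation or withdrawn consent, at their last diary entry.

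   Align SAP 5.2 with this, so that one censoring time applies to each child.

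3. **Reporting.** Give the number of children in each group. Show any plain mean or median either restricted to recovered children and labelled so, or under the same rule.

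**Cost.** Wording changes in both documents; the SAP part can be made at any time before database lock. Some caregivers keep the diary a few more days, some entries will be missing, and the reported duration may be slightly less favourable.

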The presence of bloody or purulent stool and fever above 39 degrees Celsius may indicate either the presence of invasive bacteria as a reason for diarrhea or the presence of another severe disease. In addition, Racecadotril has not been investigated in patients with antibiotic-associated diarrhea. Therefore, Racecadotril should not be administered under these conditions.

Subjects who need treatment with the above listed medication should be withdrawn from the study (see section 6).

Dietary modifications for thickening of the stools or yogurt are allowed. If needed, dietary consultation with dietitian or qualified healthcare worker is recommended in order to adapt the diet for thickening of stools or intake of yogurt.

Any intake of other medication is allowed as judged appropriate by the Investigator except those on the list of prohibited medications above.

All medication taken by the subject during the study (from signing the informed consent form through post-study follow-up) is to be recorded on the Concomitant Medication form, except for study drug.

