9.1.1 Recording of Adverse Events

Any AE should be recorded on the Adverse Events form in the CRF and source documents. In order to avoid vague, ambiguous or colloquial expressions, the AE should be recorded in standard medical terminology rather than the subject's own words. Whenever possible, the Investigator should group together into a single term signs and symptoms which constitute a single diagnosis.

The existence of or change in an AE may be concluded due to the necessity to administer a concomitant medication, from a spontaneous report of the subject, from the physical examination or from special tests like ECG, EEGs, laboratory assessments or other study specified tests (source of AE).

For each subject that has signed the informed consent and prior to study drug allocation at any dose, any change to medical status should be recorded in patient's medical file in accordance to local requirements and the medical history CRF only.

Any change to medical status, which occurs after study drug allocation at any dose in the specified study AE collection period will be handled as an (S)AE.

For each subject that has signed the informed consent but does not qualify for allocation to treatment, i.e. Screen Failure, any change to medical status (from the time of ICF signature until determination of non-qualification for the study) should be recorded in patient's medical file according to local requirements. The related medical status change information will not be reviewed by Abbott or delegated staff, and will not qualify as a study (S)AE.

Each AE, of the treatment arm, is to be evaluated for duration, severity, seriousness and causal relationship to the investigational drug. The action taken with study drug, the concomitant treatment/therapy introduced and the outcome as well as whether the event led to study termination will also be recorded.

The post-study AE collection period is defined as 30 days after the subject's safety follow-up call (collection of (S)AEs should be passive in this period unless otherwise specified).

Severity

The severity of the AE should be characterized as "mild, moderate or severe" according to the following definitions:

- Mild events are usually transient and do not interfere with the subject's daily activities.
- Moderate events introduce a low level of inconvenience or concern to the subject and may interfere with daily activities.
- Severe events interrupt the subject's usual daily activity.

Drug-Event Relationship

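### Stopping condition 3 in Protocol Section 6, read literally, needs blood and pus together, although the entry rule and Section 7.7 name either sign

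*Protocol*

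**What the plan says.** Protocol Section 6 introduces its list of six conditions with "Subjects will terminate the study at the discretion of the investigator", and adds that further diagnosis and alternative treatment follow. Condition 3 is "If the subject develops bloody and purulent stools". No other condition in the list mentions blood or pus. The rest concern prohibited or rescue medication (1), confirmed fever above 39 degrees (2), more than ten watery stools a day with apathy (4), general worsening (5) and hospitalization (6).

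Exclusion 4 in Protocol Section 5.2 reads "Subjects with bloody and/or purulent stools". The synopsis and SAP Section 3.2 word it the same way.

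Protocol Section 7.7 gives the clinical reason: "The presence of bloody or purulent stool and fever above 39 degrees Celsius may indicate either the presence of invasive bacteria" or another severe disease. After a sentence on antibiotic-associated diarrhea it concludes that "Racecadotril should not be administered under these conditions".

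**The concern.** Entry and stopping rules for the same warning sign would be expected to match. For fever they do: above 39 degrees it is exclusion 3, and once confirmed by repeat measurement it is stopping condition 2 and a withdrawal rule in Section 7.7. For the stool sign, the entry rule needs either feature and the stopping rule, taken at its word, needs both.

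The stake is safety and consistency between sites. This is a multicenter outpatient study in children aged 3 to 60 months, and the flow chart schedules no clinic visit between Day 1 and the end-of-treatment visit. If a caregiver reports blood in the stool, one site could read across from exclusion 4 and treat it as a named ground for termination, while another could apply condition 3 literally. The Section 6 list is there to tell sites which findings should prompt that decision.

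**Working it through.** The plan gives no figure to reproduce, so the check compares texts. The inputs are every statement in the two documents that names the sign:

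| Place | Connective |
|---|---|
| Protocol synopsis, exclusion 4 | and/or |
| Protocol 5.2, exclusion 4 | and/or |
| SAP 3.2, exclusion 4 | and/or |
| Protocol 7.7, reason for not dosing | or |
| Protocol 6, condition 3 | and |

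Four of the five statements accept either sign; condition 3 alone joins them.

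The next step applies each rule to the three ways the sign can appear. Exclusion 4 is blood OR pus. Condition 3, taken literally, is blood AND pus. Section 7.7 is blood OR pus, with fever taken as a separate sign (the reason is given under the objection).

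| Presentation on treatment | Exclusion 4 | Section 7.7 | Condition 3 as written | Condition 3 with *and/or* |
|---|---|---|---|---|
| Blood only | met | met | not met | met |
| Pus only | met | met | not met | met |
| Both | met | met | met | met |
| Covered | 3 of 3 | 3 of 3 | 1 of 3 | 3 of 3 |

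These are counts of logical cases, not frequencies. They locate the mismatch and say nothing about how many children it would affect.

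The last step asks what remains for a child with blood only or pus only:

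- Condition 5 applies if the "disease state worsens, e.g. dehydration or increased vomiting". Its examples are not exhaustive, so new blood could fall under it.
- Section 6 has a termination category for adverse events, and under Section 9.1.1 a change in medical status after drug allocation "in the specified study AE collection period will be handled as an (S)AE".
- A need for antibiotics leads to withdrawal, through condition 1 and Section 7.7.
- Section 7.7 itself says not to give the drug.
- The investigator has discretion throughout.

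A route to stop therefore exists. None of the other Section 6 routes names the sign.

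**The case against.** The strongest reply is that condition 3 fails only on a strict reading. The phrase can be taken to mean both kinds of stool, and beside exclusion 4 and Section 7.7 that is the likelier intent. The list is discretionary, other routes to stopping exist, and nothing in the documents shows sites acting differently. Most of this stands. It limits the point to a correction of wording and makes divergence between sites a possibility, not a demonstrated effect. It does not make the text right: discretion is exercised under the listed conditions, and a general fallback guides a site less well than a condition naming the sign.

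A reader might infer two stronger things that the documents do not support.

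- **That a child with blood alone has to stay on the drug.** The routes listed above rule this out.
- **That Section 7.7 is itself defective because it joins the stool sign to fever, leaving a child without fever uncovered.** Fever above 39 degrees stands alone as exclusion 3, as condition 2 and as a withdrawal rule earlier in Section 7.7. The passage goes on to antibiotic-associated diarrhea, another separate exclusion, and refers to conditions in the plural. It reads most naturally as a list of separate signs, so it already advises against dosing with blood alone or pus alone.

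**Conclusion.** The mismatch is real and minor. Read literally, condition 3 covers one of the three presentations that exclusion 4 covers, and it is the only one of five statements that joins the two signs. This rests on the literal reading of *and*; the intent was probably either sign, which is a reason to correct the text. The documents give no frequency for blood alone or pus alone, so the number of children affected cannot be stated and no harm is estimated. The sample-size statement and the planned analyses do not depend on condition 3. The correction is worth making because this is an operative safety rule in young children and the change brings it into line with the sponsor's own entry rule.

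**What to change.** In Protocol Section 6, condition 3, replace *and* with *and/or*. The stopping rule then agrees with exclusion 4 and with Section 7.7 on the stool sign.

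Leave Section 7.7 unchanged. Rewording it to make fever an explicit alternative is unnecessary, and would state a stand-alone fever bar without the repeat measurement that condition 2 requires.

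The edit needs no extra data, visits or analysis. The cost is procedural: Section 12.1 requires protocol changes to be documented in a written amendment with notice to the authorities, and a changed stopping rule may be classed as substantial, which would need IEC/IRB approval before sites use it. It can be bundled with other changes.
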